To address this gap in care, my program of research has comprised several studies building toward the current study: identifying Veteran primary care patients' anxiety treatment preferences, examining usual care for anxiety in PC-MHI, examining perceived feasibility of various anxiety intervention techniques among PC-MHI providers, and adapting and refining the treatment manual for the brief PC-MHI intervention for anxiety. We developed the manual by adapting evidence-based techniques from extant anxiety treatment protocols to fit the unique scope and format of the PC-MHI setting. We also incorporated our prior findings on primary care Veterans' anxiety treatment preferences to ensure the intervention is Veteran-centered. In the most recent study, we obtained preliminary feedback on the treatment manual from Veterans who received the intervention as well as PC-MHI providers who were asked to consider feasibility for real-world clinical practice. We used this stakeholder feedback to refine the treatment manual. Now we are ready to evaluate the intervention in a formal trial. Therefore, in the current study we will evaluate the effectiveness of the intervention (compared to PC-MHI usual care) in reducing symptoms of anxiety and depression. Secondary outcomes include functional impairment and quality of life as well as several potential mediating variables. We will include healthcare utilization (mental health, primary care, emergency department visits) as an exploratory outcome because individuals with anxiety disorders are known to have higher healthcare utilization, 83 which is costly to the

healthcare system.

Specific Aims

The current study is a pilot hybrid effectiveness-implementation RCT. The primary aim is to evaluate feasibility, acceptability, and effectiveness of the brief anxiety intervention compared to PC-MHI usual care. As this is a pilot study, the emphasis is on evaluating feasibility and acceptability⁷⁷, although we will also examine preliminary effectiveness by comparing the effects of the intervention to those of PC-MHI usual care on the primary outcome of anxiety symptom severity. The secondary aim is to identify potential barriers and facilitators to implementation in real-world clinical practice.

METHOD

Study design

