We will evaluate the intervention through a RCT using a hybrid I effectiveness-implementation design⁷⁹ with PC-MHI usual care as the comparison condition. We elected to conduct an effectiveness trial (with less restrictive eligibility criteria), rather than an efficacy trial, because we are not creating a brand-new treatment, but rather adapting existing evidence-based techniques into a new intervention package in a format suitable for PC-MHI. We selected PC-MHI usual care as the comparison condition given our interest in determining whether the intervention is superior to current routine PC-MHI practices. The hybrid I design is appropriate⁷⁹ because the brief anxiety intervention has strong face validity and a base of indirect evidence (from brief CBT for anxiety used in specialty mental health and PC-MHI), although it still needs to be evaluated for effectiveness in its current format. Further, addressing implementation earlier in the process will help to reduce the lag in translating research to practice, which is highly valued in VHA.

Participants

Participants will be adult Veteran primary care patients (*N*=35) at the Syracuse VA Medical Center. Eligibility criteria are as follows:

Inclusion criteria:

- (1) age 18 years or older
- (2) Veteran seen in the Syracuse VAMC primary care clinic in the past year
- (3) screen positive for current (past 2 weeks) clinically significant anxiety symptoms (≥8 on GAD-7)

Exclusion criteria:

- (1) inability to communicate in English (as assessed by study staff)
- (2) report or demonstrate hearing impairment that would preclude telephone screening (as assessed by study staff)
- (3) (a) inability to demonstrate informed consent (defined as not being able to comprehend the study description as assessed by study staff and/or not being able to answer the comprehension of consent questions),
 - OR (b) have a diagnosis of dementia or severe cognitive impairment (defined by primary care provider or self-report, or having a diagnosis in Problem List),
 - OR (c) screen positive for cognitive impairment (≥3 errors on screener)
- (4) (a) have a diagnosis of obsessive-compulsive disorder (OCD), or serious mental illness (SMI, i.e., psychotic disorders, bipolar disorder) in Problem List,
 - OR (b) have an encounter diagnosis of post-traumatic stress disorder (PTSD) within the past 2 years OR screen positive for PTSD (≥3 on PC-PTSD-5)

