Before the scheduled baseline assessment, a research assistant will mail two copies each of the Informed Consent Form and the HIPAA Authorization form to the participant before the scheduled assessment, along with a postage-paid, pre-addressed envelope so they can send the signed informed consent and HIPAA authorization forms back to study research staff at the Syracuse VAMC. The packet will also include copies of the response options for the questionnaires as well as an information sheet with relevant phone numbers for VA behavioral health services and crisis resources including the Veterans Crisis Line. The participant will be able to reference these materials during the informed consent process and will be asked to sign both forms during the telehealth appointment prior to completing any baseline questionnaires. Participants will be asked to

send back the signed informed consent and HIPAA authorization within the self-addressed envelope. No intervention sessions or follow-up assessments will occur until this documentation is received. All consent and authorization forms will be stored in the same locked file cabinets in the same offices as usual/ previously approved. All other assessments will occur via telephone, which is already an option in our standard protocol.

Randomization: Participants will be randomized to the intervention or usual care using a stratified random assignment based on anxiety severity (GAD-7 score of <15 vs \geq 15 [\geq 15 indicates severe symptoms]⁴⁴) as well as depression severity (PHQ-9 score of <15 vs 15-19 [15-19 indicates moderately severe symptoms]⁴⁶). Patients with comorbid anxiety and depression symptoms are more functionally impaired than patients with either anxiety or depression alone, so it is important to balance out the proportion of patients with worse depressive symptoms across the two conditions.

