Therapeutic alliance will be assessed at post-assessment using the 12-item Working Alliance Inventory-Short Form Revised (WAI-SR),⁸⁵ which asks patients to rate, on a Likert scale from 1 (seldom) to 5 (always), their experience of the therapist in terms of quality of the relationship bond, agreement on the goals of treatment, and agreement on the tasks of treatment. This measure has good reliability and validity.^{85,86}

Acceptability will be assessed by an acceptability interview, which we adapted from our prior work. The semi-structured interview is designed to assess Veterans' satisfaction with and perceived helpfulness of specific components of the intervention (including handouts), or for those who did not attend any intervention sessions, what prevented them from attending and how we could improve the way the treatment is described to appeal more to Veterans. It will be used to identify barriers and facilitators to engagement, adherence, and retention to guide future implementation efforts.

Table 1: Summary of Measures and Time of Administration

Measure	Construct	Telephone	Baseline	Each	Follow-up	Post-
		screening		interventi	assessm	assessm
				on	ent	ent
				session	(telephon	
					e)	
Demographics	Demographics	X	Х			
6-item screener	Cognitive impairment	X				
GAD-7	Anxiety symptom severity	X	Х	Х		X
PHQ-9	Depressive symptom severity	X	X	Х		X
PC-PTSD-5	Probable PTSD (screen)	Х				
Treatment history	Counseling/therapy and	x (past	Х			
	medication use	month)	(lifetime)			
Readiness ruler	Readiness to change		х			
OASIS	Impairment due to anxiety		х		Х	Х
ODSIS	Impairment due to depression		х		Х	Х
DASS-21	Stress / Anxiety / Depression		х		Х	Х
Q-LES-Q-SF	Quality of life		х			Х
ISI	Insomnia		х			Х
BADS-SF	Behavioral activation		х			Х
MEAQ-BA	Behavioral avoidance		х			Х
PEG	Pain intensity/interference		х			Х
Healthcare visits	Healthcare utilization		х			Х
COVID-19	COVID-19 questions		х		Х	Х
CSQ	Treatment satisfaction					Х
ERS	Treatment credibility					Х
WAI-SR	Therapeutic alliance					Х
Interview	Acceptability of intervention					Х

DATA SAFETY, MANAGEMENT, AND SECURITY

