The primary outcome is anxiety symptom severity, measured by GAD-7 scores. The primary analysis will be an analysis of covariance (ANCOVA) controlling for baseline GAD-7 score. Secondary analyses will use the same approach to evaluate effects on other pre-post outcomes (PHQ-9 and Q-LES-Q-SF). We will adjust for baseline scores, thus reducing the residual variance, and theoretically giving us increased power.

Multilevel modeling (MLM) will be used for outcomes with multiple (>2) assessment points (OASIS, ODSIS, DASS-21 subscales). MLM will be used to test the primary null hypothesis that no differences exist in the rate of change in outcomes between the intervention group and PCMHI usual care group against the two-sided alternative that differences do exist. A composite equation consisting of within- and between-person effects will be used to analyze our data. The within-person (level 1) equation estimates participants' unique intercept (time=0) and outcome trajectory. The between-person (level 2) equation estimates the average initial status at time 0 and rate of change in the outcome. Random effects include an intercept and slope. Both level-1 and 2 (subject) residuals are assumed to be normally distributed.

References

- 6. Mendlowicz MV & Stein MB (2000). Quality of life in individuals with anxiety disorders. *American Journal of Psychiatry*, *157*, 669-682.

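### Minor: randomization is stratified on GAD-7 and PHQ-9, but the primary ANCOVA adjusts only for baseline GAD-7, which may cost a little precision

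*Combined protocol and SAP*

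**What the plan says.** The Randomization paragraph under Procedure stratifies on anxiety severity (GAD-7 below 15 versus 15 or more) and adds a second factor: "as well as depression severity (PHQ-9 score of <15 vs 15-19". The reason given for the second factor is functional: "Patients with comorbid anxiety and depression symptoms are more functionally impaired than patients with either anxiety or depression alone". The paragraph then draws the consequence for the design: "so it is important to balance out the proportion of patients with worse depressive symptoms across the two conditions". It does not say whether allocation within strata is blocked, or whether the screening or the baseline score defines the strata.

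The Statistical Analysis Plan names one covariate for the primary outcome: "The primary analysis will be an analysis of covariance (ANCOVA) controlling for baseline GAD-7 score". It extends the same approach to PHQ-9 and Q-LES-Q-SF, then gives the purpose: "We will adjust for baseline scores, thus reducing the residual variance, and theoretically giving us increased power". This reads as adjusting each outcome for its own baseline. The SAP does not mention stratification, and no other section puts PHQ-9 or the strata into the GAD-7 model. Table 1 shows PHQ-9 collected at screening, at baseline and at post-assessment.

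Participants gives N=35. Specific Aims puts the emphasis on feasibility and acceptability, "although we will also examine preliminary effectiveness by comparing the effects of the intervention to those of PC-MHI usual care".

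**The concern.** The plan adjusts in order to shrink residual variance and gain power. It also treats depression severity as important enough to balance by design. Leaving baseline PHQ-9 out of the primary model forgoes a possible gain of the kind the SAP says it wants, from data it already has. Continuous baseline GAD-7 largely covers the GAD-7 stratum, so PHQ-9 is the real omission.

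What is at stake is the width of one interval in a small trial. There is no bias in the estimate and no excess of false positives.

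**Working it through.** **Inputs from the documents.** N=35; alpha 0.05; planned model arm + baseline GAD-7, so residual df = 35 − 3 = 32. Adding PHQ-9 leaves 31. The plan gives no power, effect size, SD or correlation, so it has no figure of its own to reproduce.

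**Break-even, simple allocation.** Adding a covariate with partial correlation ρ multiplies the residual variance by (1 − ρ²). It also raises the expected variance of the adjusted difference by (N−4)/(N−5) = 31/30, because the covariate is imbalanced by chance.

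- On the standard error alone: ρ² = 1 − 30/31 = 0.032, so ρ = 0.18.
- On the confidence interval, with t quantiles 2.03693 (32 df) and 2.03951 (31 df): ρ² = 1 − (30/31) × (2.03693/2.03951)² = 1 − 0.9677 × 0.9975 = 0.035, so ρ = 0.19.

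**Break-even, blocked within strata.** Stratification has already removed part of the imbalance, so the covariate costs less. By simulation, the interval breaks even at a partial R² between 0.02 and 0.03, or ρ of about 0.15.

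**Size of loss or gain.** There were 20,000 simulated trials per setting, with complete data and a two-sided test. All of the following are assumed: GAD-7/PHQ-9 correlation 0.5; standardized GAD-7 coefficient 0.4; 31% in the upper GAD-7 stratum and 21% in the upper PHQ-9 stratum; effect 0.8 SD; blocks of 4 in the four strata, or simple 1:1 allocation. Each triplet is planned model / plus PHQ-9 stratum indicator / plus continuous PHQ-9. Compare within rows only, because the planned model's own residual variance changes with the row.

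| Partial R² | Allocation | 95% half-width (SD) | Power (%) |
|---|---|---|---|
| 0 | blocked | 0.632 / 0.636 / 0.640 | 69.6 / 69.1 / 68.5 |
| 0 | simple | 0.647 / 0.658 / 0.658 | 67.7 / 66.3 / 66.4 |
| 0.04 | blocked | 0.597 / 0.595 / 0.592 | 75.4 / 75.4 / 76.0 |
| 0.04 | simple | 0.611 / 0.616 / 0.609 | 73.1 / 72.2 / 73.3 |
| 0.10 | blocked | 0.575 / 0.566 / 0.552 | 77.5 / 78.4 / 80.4 |
| 0.10 | simple | 0.588 / 0.586 / 0.568 | 76.2 / 76.9 / 79.0 |
| 0.19 | blocked | 0.551 / 0.532 / 0.501 | 81.2 / 83.2 / 87.2 |
| 0.19 | simple | 0.564 / 0.549 / 0.516 | 79.2 / 81.1 / 86.0 |

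The 0.19 rows are the case where PHQ-9 predicts as well as baseline GAD-7. With both coefficients 0.4 and correlation 0.5, R² is 0.16 + 0.16 + 2 × 0.4 × 0.4 × 0.5 = 0.48 with both scores and (0.4 + 0.2)² = 0.36 with GAD-7 alone. The partial R² is then (0.48 − 0.36)/(1 − 0.36) = 0.19.

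The continuous score changes power by −1.1 to −1.3 points at 0, +0.2 to +0.6 at 0.04, about +3 at 0.10, and +6.0 to +6.8 at 0.19. The binary indicator recovers less than half of the narrowing: at 0.19, blocked, (0.551 − 0.532)/(0.551 − 0.501) = 38%.

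**Type I error of the planned model.** At partial R² 0.10 and 0.19, runs gave 4.0 to 4.7% if blocked and 4.9 to 5.4% if simple (Monte Carlo SE about 0.15 points). The 5.4% was not repeated in further runs and is taken as simulation noise. The blocked figures show a slightly conservative test: blocking improves true precision, but the model's standard error does not reflect this when PHQ-9 is omitted.

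**Sensitivity.**

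- Strata set by the screening score (assumed correlation 0.8 with baseline), blocked, partial R² 0.10: 78.0% to 80.7% with continuous PHQ-9.
- GAD-7/PHQ-9 correlation 0.3 or 0.7 (GAD-7 coefficient 0.4 or 0.3), partial R² 0.10: gains of 2.6 to 3.1 points.
- 28 analysed (assumed 20% loss), partial R² 0.10: 67.3% to 70.3% blocked, 64.4% to 67.0% simple. The break-even correlation is then about 0.17 to 0.21.

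**The case against.** The planned model is valid and prespecified. Stratifying serves balance in its own right, the plan never promises to adjust for the strata, and one covariate at N=35 is a defensible, parsimonious choice.

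The sign of the benefit cannot be read from the documents. The partial correlation is not given, and the PHQ-9 stratum is justified by functional impairment, not by later GAD-7. Below the break-even, the change makes the primary analysis slightly worse.

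Stratification itself argues only for the binary indicator, which gains under 1 point at partial R² 0.10. The case for continuous PHQ-9 is a case for a prognostic covariate, and other baseline measures in Table 1 could be put forward the same way. At an assumed 0.5 SD effect with blocked allocation, power moves from 34.2% to 33.5% at partial R² 0, from 37.5% to 37.8% at 0.04, and from 39.9% to 43.2% at 0.10. None of this changes how a pilot is read.

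Most of this stands, and it is why the point is rated minor. It does not remove the point. PHQ-9 is the one other score the plan chose to balance, the SAP's stated reason for adjusting applies to it, and the possible loss is about 1% of the interval width (0.632 to 0.640 blocked; just under 2% under simple allocation, 0.647 to 0.658), while the gain can be several times that.

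**Conclusion.** The mismatch is real and minor. Validity is not affected: the planned estimate is unbiased and type I error is not inflated. Precision is lost only if baseline PHQ-9 predicts week-16 GAD-7 beyond baseline GAD-7, with a partial correlation above about 0.15 (blocked) to 0.19 (simple) at N=35. If so, the forgone power is about 3 points at partial R² 0.10 and 6 to 7 points at 0.19.

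These sizes rest on assumed correlations, stratum shares, effect size and allocation scheme, with all 35 analysed. Whether the correlation exceeds the break-even is plausible given the comorbidity described in the Background, but it is not shown. This is something to consider, held with medium confidence.

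**What to change.** Prespecify the primary model as week-16 GAD-7 on arm, baseline GAD-7 and baseline PHQ-9, with both scores continuous and taken at the baseline assessment. If the team prefers the simpler model, one sentence saying why PHQ-9 is omitted is an acceptable alternative. Either way, the covariate set is fixed before the data are seen.

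The cost is one SAP sentence and one residual df (32 to 31), with no new data. If PHQ-9 adds nothing, the price is about 1.1 to 1.3 points of power at N=35, and about 1.2 to 1.5 points with 28 analysed.
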